Intervention to Change Attributions that are Negative (ICAN): a New Approach to Reducing Anger and Aggression after Brain Injury

Study Protocol and Statistical Analyses Plan

Clinicaltrials.gov #: NCT03648476

Unique Protocol ID: 1806829789

Secondary IDs: 1R21HD094232-01

April 19,2021

STUDY PROTOCOL

Study Design. We will conduct a small, randomized waitlist controlled trial of the ICAN intervention to examine feasibility and acceptability (Aim 1); effect size estimates on perspective taking and hostile attributions (Aim 2); and anger and aggression (Aim 3) in participants with TBI.

Inclusion/Exclusion Criteria.

Inclusion Criteria

- History of complicated mild to severe TBI (injury due to an external physical force), with injury severity being defined *either by*¹ Glasgow Coma Score at time of injury (≤ 12), or post-traumatic amnesia (≥ 1 day), or loss of consciousness (≥ 30 minutes), or positive head CT scan consistent with TBI.
- At least 18 years of age or older;
- ≥ 1 year post-injury;
- Have adequate vision, hearing, and speech/ language skills to participate in assessments and group therapy (determined based on interaction with the participant at screening)
- Have adequate reading comprehension (due to the primary assessment involving written scenarios)
- Have abnormal scores on one or more of the below measures of negative attributions or perspective taking (determined at T0 screening):
 - Epps Intent: >4.8 , or
 - Epps Hostility: >4.2 , or
 - Epps composite score: >-0.2 , or
 - AIHQ Intent: >3.3 , or
 - IRI Perspective Taking: < 14.5 for men and < 15.5 for women
- Have above average aggression (>49 at telephone prescreening; >55 at T0 screening) on one of the Buss Perry Subscales.
- No anticipated medication changes for emotions/ behavior during length of study participation; medications for emotions/ behavior must be stable within last 30 days prior to consent at T0 (Screening)
- Have reliable mode of transportation

Exclusion criteria:

- Pre-morbid neurological disorders that could affect mood and cognition (e.g. stroke); does not include controlled seizures
- Progressive central nervous system disorders (e.g. dementia, Parkinson's)
- Developmental disability (e.g., autism, developmental delay);
- Major psychiatric disorders (e.g. schizophrenia, Borderline Personality Disorder);

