- Severe Depression and/or perceived risk to self or others (mental health resources will be provided and if suicide risk, approved suicide protocol will be utilized);
- Currently receiving active behavioral therapy for anger.
- On drug research study for irritability, anger, aggression

Note: Participants will not be excluded if they do not have caregiver.

Sample Size Calculation. Forty participants (20 per group) will be enrolled to allow for 20% dropout. Thirty-two participants (16 per group) are expected to finish the study. For Aim 1, feasibility and satisfaction percentages of 80%, a sample size of 30 will allow these proportions to be estimated to within 13% using one-sided 95% confidence intervals. For between group effect sizes for Aims 2 and 3, a sample size of 21 per group will detect an effect size of 0.9 standard deviations with 80% power using a two-sided t-test at a .05 level of significance. An ANCOVA model with pre/post correlation of 0.5 can reduce the sample size needed by 25% or to 16 per group. For within group effect sizes for Aims 2 and 3, 16 subjects will provide 80% power to detect a difference in means of .78 standard deviations using a two-sided paired t-test at the .05 level of significance.

Recruitment. The Rehabilitation Hospital of Indiana (RHI), an affiliate of Indiana University (where the PI and Co-I's have offices), will be a primary source of recruitment (see [name] LOS). IU/RHI is one of 16 nationally recognized Traumatic Brain Injury Model Systems (TBIMS) sites in the United States, making it a strong site for recruitment of this population. On average, RHI admits around 120 individuals with TBI annually; $>1,000$

individuals with TBI are seen in the RHI outpatient clinics. We will use 1) past RHI inpatients, 2) RHI Outpatient Clinic, 3) RHI Research Registry (n=295), and 4) IU/RHI TBIMS Database (>230 enrolled to date). We will recruit through letters sent by physicians to their patients, pre-clinic chart screening, clinician discussions with patients, flyers posted in RHI, recruitment videos shown around the facility, researchmatch.com and through The Rehabilitation Hospital of Indiana's Facebook page. Flyers will be distributed at TBI support groups and the Brain Injury Association of Indiana. RHI patient letters will be followed with a phone call to confirm receipt of the letter and inquire about interest in the study. See Pre-screen below.

Outcome Measures.

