Ambiguous Intentions Hostility Questionnaire: This questionnaire consists of 15 written vignettes describing actions/ situations that were intentional (5), ambiguous (5) and accidental (5). After participants read each vignette and imagine the scenario happening to her or him, they are asked five questions: 1) why the other person (or persons) acted that way toward you (open-ended response later rated by two independent raters; score indicates "hostility bias"); 2) Whether the other person (or persons) performed the action on purpose (1 "definitely no" to 6 "definitely yes") using a Likert Scale (Intent score); 3) how angry it would make them feel (1 "not at all angry" to 5 "very angry") using a Likert scale (anger score); 4) how much they would blame the other person (or persons) (1 "not at all" to 5 "very much") using a Likert scale (blame score); and 5) how she or he would respond to the situation, (open-ended response).

General Anger and Aggression: Changes in anger and aggression will be evaluated with several different measures. General anger will be measured with the Anger-Affect Scale from the NIH Toolbox Emotion Battery (also known as the Patient Reported Outcomes Measurement Information System; PROMIS) Anger Short Form), and will be a secondary outcome measure.⁸ This 5 item subjective questionnaire requires participants to indicate the frequency with which they have been bothered by anger symptoms in the past week using a 5 point Likert scale. Scores are converted to standard scores, and can be used to classify anger severity. Developed as part of NIH's initiatives for better outcomes measurement, this tool has good validity and reliability.⁸ Aggression will be measured with the Buss-Perry Aggression Questionnaire (AQ) and the AQ will be the primary outcome measure.⁹ The AQ is a standardized measure comprised of 34 statements to assess anger, hostile thoughts, and physical and verbal aggression. Participants rate statements using a 5-point scale. Raw

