and scaled scores (adjusted by age and gender) are provided for aggression subcomponents and total aggression. Total aggression will be used for our analyses. The AQ is a widely used and accepted aggression measure, including for TBI studies.¹⁰⁻¹⁴ It has good test-retest reliability (.72-.80), and good internal consistency (.76-.94).⁹ To determine the subjects' global sense of change in anger and aggression, the Patient Global Impression of Change (PGIC) regarding these outcomes will be administered. To determine global behavioral changes in anger and aggression as perceived by others, the Caregiver Global Impression of Change (CaGIC)^{4,5} will be administered to participant caregivers. Using a 7-point Likert scale, caregivers will be asked to rate the degree of change (1=no change; 7=a great deal better) in the participant's anger and aggression. The PGIC and CaGIC are considered secondary outcome measures.

Emotion Regulation: The Difficulty with Emotion Regulation Scale (DERS)⁶¹ is a 5-point Likert scale that participants use to rate the frequency they utilize self-regulation behaviors in response to general emotional distress. There are 6 subscales: Lack of Emotional Awareness, Lack of Emotional Clarity, Difficulties Controlling Impulsive Behaviors When Distressed, Difficulties Engaging in Goal-Directed Behavior When Distressed, Non-acceptance of Negative Emotional Responses, and Limited Access to Effective Emotion Regulation Strategies. Items are summed to provide a Total Emotion Dysregulation score. The DERS has high internal consistency, test-retest reliability, and good construct validity.⁶¹ Importantly, because this measure assesses difficulties regulating all types of emotions, it captures different information than that provided by measures specific to anxiety, anger, or depression which can miss more general, yet common, self-regulation problems.

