Randomization and Stratification. Participants will be randomized to group after T1 testing by the study statistician using a random number generator. Randomization will be blocked and stratified by gender due to expected gender differences in hostility bias. For each treatment wave, ~6-10 participants will be randomly assigned to ICAN or WLC. Once ~6-10 eligible participants have been identified and completed Time 1 testing, the statistician will assign treatment allocation to ICAN or WLC. An unblinded RA will notify the subject of their group allocation. This method will allow blinded Research assistants to remain blinded to group assignment. After the 4-7 waves, 20 participants will have been randomized to ICAN and 20 to WLC (n=40).

Intervention Procedures and Treatment Fidelity. Participants randomized to ICAN will start treatment after Time1. For WLC participants, their treatment will be delayed until after Time 2 data collection. ICAN will be delivered over six sessions each lasting approximately 2 hours, once a week in a group setting (n=5 participants/ group), for 6 weeks by 1-2 clinical facilitators. Participants will be given a notebook with information and exercises. **Treatment Fidelity.** Steps from an adapted Treatment Fidelity Checklist (NIH Behavior Change Consortium working group on treatment fidelity,²⁶) will be used to ensure fidelity of Theory, Provider Training, Treatment Implementation, Treatment receipt, and Treatment Enactment. **Specific to Training:** Facilitators will have a minimum of 2 years of brain injury experience and clinical experience. Facilitators will be trained by the PI and study consultant, [name] (ICAN creator; see LOS), which will involve reviewing a treatment manual and role-play of the ICAN exercises. The treatment manual will consist of a power point presentation outlining treatment procedures and activities, which will also be used to guide the treatment sessions with the subjects. **Delivery.** For all sessions, the power point presentation outlining treatment procedures and activities will be followed and an implementation checklist will be completed.

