Satisfaction Survey (CSQ8): To encourage honest feedback and ensure blinding of RA's, an unblinded RA will be responsible for collecting data on the CSQ-8 within approximately 1-2 weeks of completing the intervention (proximal to Time 2 for ICAN subjects and Time 3 for WLC subjects). In the case of withdrawal from treatment, the CSQ-8 may be conducted upon withdrawal from treatment, if the participant is agreeable. If participants withdraw, reasons for withdraw will attempt to be collected. At the end of the CSQ-8, the participant is presented with an optional comments section regarding their feedback and thoughts about what they liked/ did not like about the program.

Post-Treatment Qualitative Interview: To encourage honest feedback and ensure blinding of RA's, an unblinded RA will be responsible for administering the post-treatment Interview with the participant over the phone, via mail, email or in person within 1-2 weeks of completing treatment (proximal to Time 2 for ICAN subjects and Time 3 for WLC subjects).

Statistical Analysis Plan.

Primary Analyses. For Aim 1, the proportion of participants who complete at least 5 out of 6 sessions, and the proportion of participants who have satisfaction ratings that are average or higher on the standardized CSQ-8 will be calculated. For between group comparisons for Aims 2 and Aim 3, the primary analysis will be ANCOVA models with T2 measures as the outcomes, treatment group as the explanatory variable, and covariates of wave and T1 outcomes (except CaGIC which will not have T1 data since it is only collected at T2). Effect sizes (ω^2) will be calculated.

Secondary Analyses. WLC control outcomes at T2 will be compared to T1 for the ICAN and WLC group. If there are no significant differences, secondary analyses combining the data from the two treatment groups (assessments before and after intervention) will include ANCOVA, paired t-tests, and estimating effect sizes.

Missing Data. We will compare all baseline variables between subjects who drop out of the study to those who don't using two-sample *t* tests, chi-square tests or their non-parametric equivalents as appropriate. Also, we will collect as much information regarding reasons for missing data as possible. If we find that the missing data appear to be not at random, this important information will be used in designing the larger trial. Because of the small sample size, we will not attempt to model the missing data mechanism in this study.

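### Randomisation is stratified by gender but the Aim 2 and 3 ANCOVA leaves gender out: adding it aligns the model with the design, for a small and uncertain gain

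*Combined protocol and SAP*

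**What the plan says.** Under Randomization and Stratification: "Randomization will be blocked and stratified by gender due to expected gender differences in hostility bias". Under Statistical Analysis Plan, Primary Analyses, the between-group model for Aims 2 and 3 is an ANCOVA of the T2 measure with "treatment group as the explanatory variable, and covariates of wave and T1 outcomes". Gender is not listed there, nothing elsewhere adds it, and no reason is given for the omission.

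Four other places bear on which outcomes could be affected:

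- **Attribution measures.** The Inclusion Criteria use one threshold for both genders, for example "AIHQ Intent: >3.3". Table 1 lists attributions under Aim 2 with no primary or secondary mark.
- **IRI perspective taking.** The threshold differs by gender: "IRI Perspective Taking: < 14.5 for men and < 15.5 for women".
- **AQ, the primary outcome.** Eligibility reads "Have above average aggression (>49 at telephone prescreening; >55 at T0 screening) on one of the Buss Perry Subscales". Under General Anger and Aggression, "The AQ is a standardized measure comprised of 34 statements to assess anger, hostile thoughts, and physical and verbal aggression", and raw scores and "scaled scores (adjusted by age and gender) are provided for aggression subcomponents and total aggression". The total is to be analysed, but the text does not say whether raw or scaled.
- **Sample Size Calculation.** "An ANCOVA model with pre/post correlation of 0.5 can reduce the sample size needed by 25% or to 16 per group".

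**The concern.** The plan expects gender to matter for hostility bias, builds that into the allocation, and then does not carry it into the analysis. Wave, the other unit within which participants are allocated, is in the model.

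Stratification balances gender between arms, so gender adds little to the true sampling error of the treatment effect. A model without gender still counts any remaining gender variance as residual noise. Its reported standard error is then somewhat too large. What is at stake is a little precision in a trial whose purpose is to estimate effect sizes, and a clear match between design and analysis.

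**Working it through.** **1. The plan's own figures.** A two-sided t-test at 0.05 with an effect of 0.9 SD and 80% power needs 20.4, so 21 per group. The ANCOVA factor is 1 - 0.5² = 0.75, and 21 × 0.75 = 15.75, so 16 per group. Enrolment is 32 / (1 - 0.2) = 40. All three reproduce.

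**2. How much gender variance baseline leaves behind.** Let the gap be d within-gender SDs, equal at baseline and T2. Let p be the proportion of women and v = d² p(1-p). With a within-gender correlation of 0.5, the residual variance is:

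- with gender in the model: 0.75
- without gender: 1 + v - (0.5 + v)²/(1 + v) = (0.75 + v)/(1 + v)

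The share of post-baseline variance due to gender is therefore 0.25v / (0.75 + v).

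- d = 0.5: v = 0.0525 (30% women) or 0.0625 (50% women); share 1.6% or 1.9%.
- d = 0.8: v = 0.1344 or 0.16; share 3.8% or 4.4%.

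**3. The gap a given share s would need.** Inverting gives v = 0.75s / (0.25 - s).

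- s = 5%: v = 0.1875, d = 0.87-0.94 SD
- s = 10%: v = 0.5, d = 1.41-1.54 SD
- s = 20%: v = 3, d = 3.46-3.78 SD

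**4. Power change from adding gender.** This comes from a simulation of 20,000 trials per setting, each trial analysed with and without gender. Assumptions: 40 randomised in permuted blocks of 2 or 4 within gender, 4-7 waves, 12 or 20 women, four random dropouts per arm, true effect 0.9 SD, baseline in the model. The simulation error of the power difference is 0.11-0.21 points.

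| Stable gap | Change in power (points) |
|---|---|
| 0.2 SD | -0.8 to -0.2 |
| 0.3 SD | -0.7 to -0.1 |
| 0.5 SD | -0.3 to +0.3 |
| 0.8 SD | +0.5 to +1.1 |
| gender explains nothing after baseline | -1.0 to -0.3 |

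**5. Validity without gender.** Bias is under 0.01 in every setting. At a 0.8 SD gap the type I error is 4.6-4.9%. With 5 waves, the true SD of the estimate there is 0.325 with or without gender, and the mean reported SE is 0.324 without and 0.319 with it.

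**6. Omega-squared for treatment.** The full form moves by at most 0.003 in any setting. The partial form moves by +0.001 to +0.002 at 0.5 SD and +0.004 to +0.006 at 0.8 SD. The SAP does not say which form is meant.

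**7. Scope by outcome.**

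- *Epps and AIHQ attributions:* hostility bias is the stated reason for stratifying, and nothing in the documents removes a gender gap from the score.
- *IRI:* the thresholds differ by 15.5 - 14.5 = 1.0 point. If the SD is 3-6 points (assumed), that is 0.17-0.33 SD, and the change in power is about -0.8 to -0.1 points.
- *AQ total:* a raw subscale score above 55 needs at least 12 five-point items, and 4 × 12 = 48. A score above 49 needs 10 items, and 4 × 10 = 40. The scale has 34 items, so these thresholds cannot be raw scores on all four domains. Eligibility evidently uses the gender-adjusted scaled scores. If the analysed total is scaled too, no gain is expected.
- *PROMIS Anger:* a secondary outcome with a T1 value, but the documents give no basis for a size.
- *PGIC and CaGIC:* these rate change, so a stable gap in level cancels. No claim is made for them.

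**The case against.** The strongest reply is that almost nothing is lost. At 0.5 SD the gain has no clear sign. At 0.8 SD the true precision is the same with or without gender, and the average reported SE is hardly conservative. With 32 completers and 4-7 waves, wave already uses 3-6 degrees of freedom, so a smaller model is defensible in a feasibility trial. The outcomes with the best case carry no primary or secondary mark. The single attribution threshold could equally mean that no gender-specific one was thought necessary. The fix also adds gender to IRI and AQ, where no gain is expected.

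Most of this stands, and it limits the point to a small one. It does not remove the mismatch: the plan stratifies on a factor it expects to matter, omits it from the model, and does not say why. Applying one model to all outcomes with a baseline follows from how the trial randomises, not from an expected gain on each outcome.

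A reader might infer more than the documents support:

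- **That the test is invalid or the estimate biased.** Any error is in the conservative direction.
- **That 16 per group fails.** The stated figures reproduce. Simulated power was 76.8% without gender and 76.1% with it (5 waves, 30% women, no gender effect after baseline), so the level below 80% in that simulation is not caused by omitting gender.
- **That gains of 3 to 8 points are available.** They appear at post-baseline shares of 10-20% (+2.8 to +7.6 points), which need stable gaps of about 1.4-3.8 SD. Only a gap that changes after baseline could produce them otherwise, and the documents expect a gender difference in hostility bias, not in its change.

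**Conclusion.** The point holds as a low-cost alignment of analysis with design. Omitting gender makes standard errors and p-values slightly conservative if gender still predicts T2 after baseline, and has no adverse effect if it does not. The expected power change from adding it is about nil at a 0.5 SD gap and about 1 point or less at 0.8 SD.

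These sizes rest on the plan's correlation of 0.5 and 16 completers per arm. They also rest on assumptions the documents do not supply: 30-50% women, a stable gap, random dropout and the block scheme. The point is worth considering and is not a flaw in the sample size or the estimate.

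**What to change.** In the SAP, make gender a prespecified fixed covariate in the between-group ANCOVA for every Aim 2 and 3 outcome with a pre-treatment value: T2 outcome ~ treatment + wave + gender + baseline value. Compute omega-squared from that model and state whether it is the full or the partial form. State also whether the AQ total is the raw or the scaled score. If a smaller model is preferred, give the reason for leaving out the stratification factor.

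The cost is one term and one degree of freedom, about 0.3-1.0 points of power if gender explains nothing after baseline. No new data are needed.

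### Aims 2 and 3 are to deliver effect size estimates, but for the between-group ANCOVA the SAP names only ω², which has no sign, no planned interval and no stated form, and is not on the SD scale used for planning

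*Combined protocol and SAP*

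**What the plan says.** Study Design sets the trial up to give "effect size estimates on perspective taking and hostile attributions (Aim 2); and anger and aggression (Aim 3) in participants with TBI". For Aims 2 and 3 the estimate is therefore the deliverable.

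Sample Size Calculation works in SD units. Between groups, "a sample size of 21 per group will detect an effect size of 0.9 standard deviations with 80% power using a two-sided t-test", and then "An ANCOVA model with pre/post correlation of 0.5 can reduce the sample size needed by 25% or to 16 per group". Within group, "16 subjects will provide 80% power to detect a difference in means of .78 standard deviations using a two-sided paired t-test".

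The Primary Analyses paragraph of the SAP models each T2 outcome by ANCOVA on group, adjusting for wave and the T1 value. CaGIC is excepted because it has no T1 value. The paragraph ends: "Effect sizes (ω^2) will be calculated". No adjusted difference, standardized difference or confidence interval is named for Aims 2 and 3. Secondary Analyses also promise effect sizes, without naming a metric, and only if a preceding comparison shows no significant differences.

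Tables 1a and 1b show that PGIC and CaGIC are first collected at T2. Table 1a places the pre-treatment Buss-Perry (AQ) and Epps assessments at T0, where they also decide eligibility.

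**The concern.** An effect estimate from a small trial should show which arm did better, by how much, and how uncertain that is. ω² is a share of variance. It takes the same value for benefit and for equal harm, and a single value carries no measure of precision.

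The form also matters. Partial ω² takes the variance explained by the covariates out of its denominator; total ω² does not. If the partial form is meant, a value can be turned back into SD units only when the covariate correlation is known. An outcome adjusted for its T1 value then cannot be compared on this scale with one that has none. The SAP does not say which form it means.

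At stake is whether the named result for Aims 2 and 3 can be read on the scale on which the trial was planned.

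**Working it through.** **Inputs from the documents.** Difference d = 0.9 SD; two-sided α = 0.05; 80% power; pre/post correlation ρ = 0.5; 16 per group (N = 32 completers); 4 to 7 waves. Values of ρ other than 0.5 are assumptions used to show a range. Variance explained by wave is set to zero.

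**1. The plan's own figure.** The two-sample t-test calculation (noncentral t) gives n = 20.39, so 21 per group. The ANCOVA factor is 1 − ρ² = 0.75, and 21 × 0.75 = 15.75, so 16 per group. Power at 16 per group is 81.2%, or 80.4% to 80.8% after spending degrees of freedom on 7 to 4 waves. The figure reproduces.

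**2. Direction.** With residual variance 1 − ρ²:

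- F = [d²/(1 − ρ²)] × 16/2 = (0.81/0.75) × 8 = 8.64
- sample partial ω² = (F − 1)/(F − 1 + N) = 7.64/39.64 = 0.193

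Because d enters squared, +0.9 and −0.9 give the same 0.193.

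**3. Partial or total.** For equal arms and within-group SD 1, d²/4 = 0.2025.

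- total ω² = 0.2025/(0.2025 + 1) = 0.168 at every ρ
- partial ω² = 0.2025/(0.2025 + 1 − ρ²)

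| ρ | 0 | 0.3 | 0.5 | 0.7 | 0.8 |
|---|---|---|---|---|---|
| partial ω² at d = 0.9 | 0.168 | 0.182 | 0.213 | 0.284 | 0.360 |
| size of d implied by partial ω² = 0.213 | 1.04 | 0.99 | 0.90 | 0.74 | 0.62 |

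The second row uses d = 2√[ω²(1 − ρ²)/(1 − ω²)]. It shows what is lost if partial ω² is reported without ρ. The unstated form matters too: a value of 0.168 means 0.90 SD if total, but 0.78 SD if partial with ρ = 0.5.

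Across the plan's own outcomes, a 0.9 SD effect on CaGIC (no T1 covariate) has partial ω² of 0.168. The same 0.9 SD effect on an outcome with a T1 covariate at ρ = 0.5 has 0.213.

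**4. Precision.** The standard error of the adjusted difference in SD units is √(0.75 × 2/16) = 0.306. Error degrees of freedom are 26 with 4 waves and 23 with 7. The 95% half-width is 2.056 × 0.306 = 0.63 or 2.069 × 0.306 = 0.63. An observed 0.9 would be reported as 0.9 (0.27 to 1.53).

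This treats the SD as known. Allowing roughly for its estimation on 30 df adds 0.81/60 = 0.0135 to the variance of 0.09375. The standard error becomes √0.10725 = 0.327 and the half-width about 0.67 to 0.68.

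In 5,000 simulated trials at a true 0.9 SD and ρ = 0.5 (4 waves), sample partial ω² had mean 0.20 and a central 95% range of −0.004 to 0.462. A lone value shows none of that spread.

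**The case against.** The strongest reply is that the SAP is brief and does not say that ω² is all that will be reported. The ANCOVA it specifies already yields a signed group coefficient and a standard error, so benefit and harm would be confused only if ω² were published without means or coefficients. That is fair. What remains is that the plan commits to neither the coefficient nor an interval, although the estimate is the aim.

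Four stronger readings are tempting, and the documents do not support them.

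- *A reader might infer that ω² cannot be compared with 0.9 SD or used to size a later trial.* It can. Partial ω² = 0.213 gives f² = 0.213/(1 − 0.213) = 0.27, and f² × N = 0.27 × 32 = 8.64, the noncentrality behind the 80.4% to 80.8% power in step 1. What is lost is the sign and, without ρ, the return to SD units.
- *A reader might infer that ω² depends on the baseline correlation in any form.* That holds for the partial form. The population total form is 0.168 at every ρ examined.
- *A reader might take negative ω² estimates as a fault of the metric.* With these inputs they occur for observed differences below about 0.31 SD in size (F < 1). That is how a bias-adjusted estimator behaves near zero; a signed difference would be just as noisy there.
- *A reader might infer that the documents declare the estimate to be for a later trial.* A larger trial is mentioned only under Missing Data.

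**Conclusion.** The point holds in limited form. For the between-group ANCOVA of Aims 2 and 3, the only effect size named is ω², with its form unstated and no interval planned. It cannot show direction: ±0.9 SD both give 0.193. If partial, a value of 0.213 corresponds to anything from 0.62 to 1.04 SD over the assumed ρ range of 0.8 to 0, and it is not comparable between outcomes with and without a T1 covariate. The interval that would accompany an SD-scale estimate is about ±0.63 SD.

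These figures rest on 16 completers per arm, ρ = 0.5 unless stated, no wave effect and, for ±0.63, a known SD. The design, sample size, test and data collection are unaffected. This is a cheap improvement.

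**What to change.** In Primary Analyses, for each Aim 2 and Aim 3 outcome:

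- Name the ANCOVA-adjusted T2 mean difference (ICAN minus WLC), in raw units with 95% CI, as the main effect estimate. State for each outcome which sign favours ICAN, since a higher score is better on IRI Perspective Taking and worse on the AQ.
- Add a standardized difference with 95% CI and a stated standardizer that exists for every outcome, for example the pooled within-group T2 SD. A baseline SD does not serve: PGIC and CaGIC have no baseline, and the AQ and Epps baselines come from the eligibility screen, which may restrict their spread.
- Keep ω² as a supplement, saying whether it is partial or total.

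In Secondary Analyses, report within-group mean change with 95% CI.

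The cost is a few sentences in the SAP and a few more output columns, with no new data, participants or models. The intervals will be visibly wide. A T2 standardizer can itself be affected by treatment if ICAN changes the spread of scores, which is why the raw-unit difference should come first.
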